4.2 Analysis Populations

4.2.1 Analysis Populations

- **Intent to Treat (ITT):**

All subjects randomized to the study. This will include subjects who underwent the study device placement procedure, regardless of whether the study device was successfully placed or not.

- **Safety:**

All subjects who undergo a successful study device placement procedure.

- **Evaluable for Pregnancy (EP):**

Safety subjects who had VeraCept or Paragard placed successfully and meet requirements 1, 2 and 3 as follows.

1. Be post-menarcheal up to 35 years of age (inclusive) at enrollment
2. Have at least one report of pregnancy status after being enrolled
3. Do not have pre-treatment pregnancy, which is defined as the estimated conception date being before the insertion date.

Subjects with major protocol violations that are deemed to have had a material impact on the assessment of the pearl index will be excluded from the EP analysis population.

Exclusions based on major protocol deviations will be reviewed and approved by Sebela and its designee.

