4.1.2 Reference Date and Study Day Calculation

A subject could have 2 study device insertion attempts, which could be on different dates. The following 2 study reference dates will be defined to meet the analysis requirements specified in this SAP.

- First study reference date=date of the first insertion attempt
- Second study reference date=date of successful insertion

The first study reference date will be used for Intent-to-Treat (ITT) analysis to include all data since first device insertion attempt regardless of insertion success or failure (e.g., AEs related to replacement procedure).

The second study reference date will be used to define exposure period and analysis visit windows for all cycle-based analysis and analysis for data with scheduled data collection.

The second study reference date is Day 1 of Cycle 1.

For both reference dates, study day will be calculated as follows:

If event date \geq study reference date:

$$\text{Study day of event} = \text{Event date} - \text{Study reference date} + 1$$

If event date $<$ study reference date:

$$\text{Study day of event} = \text{Event date} - \text{Study reference date}$$

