4.1.7 Adverse Event

4.1.7.1 Definition of an Adverse Event

An AE is any untoward medical occurrence in a clinical investigation where a subject has been administered an investigational product and which does not necessarily have a causal relationship with this treatment.

The analysis of AEs will be based on the principle of treatment emergence. Treatment-emergent AEs (TEAEs) will be defined as events that occur (or worsen) on or after the first treatment date of the insertion of the device.

In this study, Pregnancy is an outcome, and not an AE.

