4.1.7.3 Adverse Events of Specific Interest

Adverse events of particular clinical importance (other than SAEs) will be classified as AEs of specific interest (AESIs). For this study, AESIs refer to reports of pain during insertion, pelvic infection (e.g., pelvic inflammatory disease or endometritis), dysmenorrhea, abdominal pain, expulsion, and uterine perforation. AESIs will be identified and assessed by the Medical Monitor during the ongoing monitoring of safety data during the trial, and for the CSR. For each AESI, a narrative may be written and included in the CSR.

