4.11 Safety and Tolerability

Adverse events will be coded and classified by system organ class (SOC) and preferred term (PT) using the Medical Dictionary for Regulatory Activities (MedDRA) version 24.0. The summaries of AEs will be limited to TEAEs. Number (%) of subjects reporting AEs and SAEs will be summarized for the Safety population.

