4.11.1 Brief Summary of Adverse Events

The number (%) of subjects reporting any of the following events during the study will be reported in the brief summary of AEs for the Safety population:

- AE
- AE related to study device
- AE related to study device placement/removal procedure
- SAE
- SAE related to study device placement/removal procedure
- AE leading to study device removal
- AE leading to study discontinuation
- AE leading to Death

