4.11.2 Adverse Events by System Organ Class and Preferred Term

The incidence of Treatment-Emergent Adverse Events (TEAE) and SAEs will be summarized by MedDRA primary SOC and PT. The summary will include the total number and percentage of subjects reporting an AE within an SOC and/or PT.

The incidence of TEAEs by SOC and PT by maximum severity for the Safety population will be presented.

Incidence of TEAEs by SOC and PT by closest relationship to study device for the Safety population will be presented.

The incidence of TEAEs by SOC and PT by closest relationship to drug placement/removal procedure for the Safety population will be presented.

The incidence of Treatment-Emergent SAEs by SOC and PT by closest relationship to drug placement/removal procedure for the Safety population will be presented.

Incidence of TEAEs experienced by at least 10% of subjects by SOC and PT for the Safety population

Incidence of AESIs (pain during insertion, pelvic infection (Pelvic Inflammatory Disease or endometritis), expulsions and uterine perforations), which includes the following MedDRA preferred terms: abdominal pain, abdominal pain lower, abdominal pain upper, pelvic inflammatory disease, procedural pain, device expulsion, dysmenorrhea following IDU placement, dysmenorrhea-post-procedural, embedded device, insertion pain, intermittent dysmenorrhea, post procedural dysmenorrhea, uterine perforation, worsening of dysmenorrhea, endometritis, post procedural discomfort, pelvic discomfort and pelvic pain will be summarized for the Safety population.

Incidence of Allergy-Related AEs, based on Medical Monitor review, will be summarized by PT and relationship to study device will be presented in the Safety population.

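### Any woman whose device placement was attempted but never succeeded would be absent from every AE incidence table, including those on harms of the insertion itself

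*SAP*

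**What the plan says.** The safety SAP, section 4.2.1, defines two relevant sets.

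- The Safety set is "All subjects who undergo a successful study device placement procedure".
- The ITT set is everyone randomized, and it covers women who had the procedure "regardless of whether the study device was successfully placed or not".

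The AE incidence tables use the first set.

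- Section 4.11: "Number (%) of subjects reporting AEs and SAEs will be summarized for the Safety population".
- Section 4.11.1 lists AEs and SAEs related to the placement or removal procedure among the rows that "will be reported in the brief summary of AEs for the Safety population".
- Section 4.11.2: "The incidence of TEAEs by SOC and PT by closest relationship to drug placement/removal procedure for the Safety population will be presented". The matching SAE table and the AESI table are also on the Safety set.
- Section 4.1.7.3 shows why the AESI table matters here: "AESIs refer to reports of pain during insertion, pelvic infection", with uterine perforation later in the same list.

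Section 4.1.2 sets up two reference dates. The first, the date of the first insertion attempt, is for an ITT analysis "to include all data since first device insertion attempt regardless of insertion success or failure". Its bracketed example is AEs of the procedure, although the printed word is replacement, not placement. No table in 4.11 is specified for the ITT set.

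On the protocol side, randomization is on the day of the first attempt (11.2). A second attempt may follow the same day or within a week, and a second failure ends participation (6.1.2, 11.2). AEs during placement are recorded (7.4.1).

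**The concern.** For insertion pain, perforation and other harms of the procedure, the exposure is the attempt. Whether the attempt succeeds is known only afterwards, and the harm may be the reason it failed. A denominator restricted to successes gives the incidence in a group selected by the outcome of the procedure under study. It can drop the women in whom a serious insertion event is most relevant.

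What is at stake is a descriptive by-arm incidence of insertion harms. A zero in the table could be true of the placed women and untrue of the women in whom the device was attempted. The placement table (4.9, 4.9.1.1) counts failed first and second insertions with ITT among its populations, so two tables about the same procedure would rest on different women.

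**Working it through.** **Can such a woman exist, and where would she be counted?**

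1. She is randomized on the day of the first attempt (Protocol 11.2), so she is in ITT.
2. Both attempts fail and she is withdrawn (Protocol 6.1.2, 11.2). She has no successful placement, so she is not in Safety (safety SAP 4.2.1).
3. An AE during either attempt is recorded (Protocol 7.4.1).
4. Every AE incidence table is on Safety (4.11, 4.11.1, 4.11.2), so neither she nor her event is counted there.
5. A woman whose second attempt succeeds is in Safety and is not affected.

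**Arm size.** The plan needs 12 evaluable per group and allows for 40% unevaluable: 12 / (1 − 0.40) = 20 per group, as stated in Protocol 11.1. The concern does not otherwise depend on the sample-size calculation.

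**Size of the effect.** The documents give no placement-failure rate and no AE rate, so the inputs below are assumptions. In one arm let N = women attempted, m = never placed, x = placed women with the event, y = never-placed women with the event. Then

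shift = (x + y)/N − x/(N − m) = (m/N) × [y/m − x/(N − m)].

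The bracket is a difference of two proportions and lies between −1 and +1, so the shift is at most m/N in either direction. For m = 1 and N = 20 that is 1/20 = 5 percentage points. If m = 0 the two sets coincide and the shift is 0.

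| Assumed case (m = 1) | Safety set | All attempted | Shift (points) |
|---|---|---|---|
| Perforation in the never-placed woman only, N = 20 | 0/19 = 0% (0 to 17.6%) | 1/20 = 5.0% (0.1 to 24.9%) | +5.0 |
| Same, and she is replaced, N = 21 | 0/20 = 0% (0 to 16.8%) | 1/21 = 4.8% (0.1 to 23.8%) | +4.8 |
| Pain in 4 placed women and in her, N = 20 | 4/19 = 21.1% (6.1 to 45.6%) | 5/20 = 25.0% (8.7 to 49.1%) | +3.9 |
| Pain in 4 placed women, not in her, N = 20 | 4/19 = 21.1% (6.1 to 45.6%) | 4/20 = 20.0% (5.7 to 43.7%) | −1.1 |

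Intervals are exact (Clopper-Pearson) 95%. Replacement within the same treatment is allowed by Protocol 4.4.

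**How likely is at least one such woman?** For an assumed never-placed rate q, the chance among 40 women is 1 − (1 − q)^40. This gives 33% at q = 1%, 87% at 5% and 98.5% at 10%. These figures show only how the answer depends on q; the documents do not indicate which q applies.

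**The case against.** The strongest reply is that little is hidden. With about 40 women, 4.11.4 provides a complete AE listing, plus separate listings of SAEs, AESIs and procedure-related AEs. Section 4.11.3 provides narratives of SAEs and AESIs. Disposition with reasons (4.5) and failed insertions (4.9.1.1) are reported for ITT. A perforation at a failed attempt would be listed and narrated. Safety comparisons are descriptive (4.4), safety is not an endpoint (2.2), and a set of women who received the device is a sensible basis for device-related, expulsion and long-term events. All of this stands and keeps the point minor. It does not supply an incidence by arm for the procedure.

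A second reply is that 4.1.2 defines a date and does not promise an ITT table of AEs, and that its example is oddly printed. This also stands in part. The stated purpose, to include data whatever the insertion outcome, is clear, but no AE table carries it out.

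A third reply concerns the remedy. Moving the whole AESI table to attempted placements would be wrong. Its preferred-term list includes device expulsion and embedded device, which a never-placed woman cannot have. It also includes pelvic infection and dysmenorrhea terms, for which she is not followed after withdrawal; counting her there would dilute the rate. The same holds for removal-related events. This is correct, and the fix is limited accordingly.

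A reader might infer that the timing rule also excludes these events, because 4.1.7.1 counts AEs "on or after the first treatment date of the insertion of the device". That wording is loose, but the date imputation rules (4.1.8) and the listing (4.11.4) work from the first insertion, and 4.1.2 defines the first-attempt date. The exclusion comes from the population definition.

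**Conclusion.** The point holds and is minor. As written, any randomized woman with an attempted but never successful placement would be absent from the numerator and denominator of every AE incidence table, including those on harms of the attempt. This follows from the stated definitions and needs no assumption. Its numerical effect does: it is nil if no such woman occurs, and at most 5 points in either direction for one among 20.

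Three stronger readings are tempting and are not supported.

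- That these events go unreported: they remain in the listings and, if SAEs or AESIs, in the narratives.
- That the tables understate insertion harm or favour one device: the direction is unknown, as the −1.1 point case shows, and the intervals overlap widely.
- That the primary comparison is affected: the PK populations require successful placement by their own definitions, and the PK results do not use the Safety set.

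**What to change.** In 4.11.1 and 4.11.2 of the safety SAP, add one supplementary summary by arm for all randomized women with an attempted placement (the ITT subjects attempted), counted from the first study reference date of 4.1.2. It should contain:

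- AEs and SAEs related to the placement procedure;
- the insertion AESI terms only, namely insertion or procedural pain and uterine perforation.

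Keep the Safety set for all other tables, including removal-related events, expulsion, embedded device, pelvic infection, dysmenorrhea, device-related and allergy-related AEs, exposure and visit-based summaries. Add a footnote with the number of never-placed women by arm. If that number is zero, the footnote shows that the two denominators agree.

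The cost is small. ITT and its by-arm columns already exist (4.2.1, 4.4), and the AEs are already collected, so no new data are needed. The SAP tables combine placement and removal in one category. If the database does too, events in placed women would have to be separated by date; the documents do not show how the field is built. The downside is a second denominator that must be clearly labelled, and insertion-event rates that may move slightly in either direction.

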4.3 Analysis Population Subgroups

No subgroups will be analyzed.

4.4 General Data Presentation Plan

Analyses will be conducted using SAS® software, Version 9.4 or above (SAS Institute Inc, Cary, NC).

Unless otherwise specified, the table summary for the main study will display the following columns:

Analysis Population	Table Display Columns		
ITT	VeraCept	Paragard	Overall
Safety	VeraCept	Paragard	Overall
EP	VeraCept		

In general, all efficacy and safety variables will be summarized using descriptive statistics and graphs as appropriate. Continuous variables will be summarized by descriptive statistics (sample size (n), mean, SD, minimum, median, and maximum). Categorical variables will be summarized in frequency tables (frequencies and percentages).

Means and medians will be displayed with 1 more decimal place than the collected data, and SDs will have 1 more decimal place than the means and medians. Minimum and maximum will be displayed with the same number of decimal places as the collected data. Percentages will be rounded to 1 decimal place.

No formal statistical testing will be performed on demographic, baseline characteristic, or safety data unless stated otherwise for a specific parameter in the SAP. Point estimates will be presented with their 95% confidence intervals (CIs) where appropriate.

Only observed data, with no data imputation, will be used for the efficacy analyses unless otherwise specified. Safety analyses will also be conducted on the observed data. However, the worst-case scenario will be applied for the start date/time of an AE or medication that is partially or completely missing. That is, the AE will be assumed to be treatment emergent, and the medication will be considered concomitant.

4.5 Disposition of Subjects

Disposition of subjects will be summarized for the ITT population.

A disposition table will report the following:

- The number and percentage of subjects in each analysis population
- The number and percentage of subjects who discontinued the study prior to Day 57, including the reasons for discontinuation
- The number and percentage of subjects who completed Day 57

- The number and percentage of subjects who discontinued the study after Day 57 but prior to 1 year of use, including the reasons for discontinuation
- The number and percentage of subjects who complete 1 year of use
- The number and percentage of subjects who discontinued the study after 1 year of use but prior to 2 years of use, including the reasons for discontinuation
- The number and percentage of subjects who completed 2 years of use
- The number and percentage of subjects who discontinued the study after 2 years of use but prior to 3 years of use, including the reasons for discontinuation
- The number and percentage of subjects who completed 3 years of use
- The number and percentage of subjects who discontinued the study after 3 years of use but prior to 4 years of use, including the reasons for discontinuation
- The number and percentage of subjects who completed 4 years of use
- The number and percentage of subjects who discontinued the study after 4 years of use but prior to 5 years of use, including the reasons for discontinuation
- The number and percentage of subjects who completed the study (5 years of use)

Listings will be generated for the following:

- Subject's disposition
- Subject's membership in each analysis population and reason for exclusion from each analysis population

4.6 Protocol Deviations

Number (%) of subjects with major protocol deviations will be summarized and deviation type for the ITT population. Details about each protocol deviation (major/minor) will be presented in the protocol deviation listing.

4.7 Baseline Demographics and Characteristics

Baseline demographics will be summarized for the ITT, EP, and Safety populations. All other baseline characteristic information will be summarized for the ITT population only.

4.7.1 Baseline Demographics

The following variables collected at Screening/Baseline will be included in the baseline demographics summary table:

- Age (years) at enrollment
- Age group at enrollment (≤ 35 years old, 36-45 years old)
- Ethnicity
- Race
- Marital status at enrollment
- Weight (kg) at enrollment

- Height (cm) at enrollment
- Body mass index (BMI) (kg/m²) at enrollment
- BMI group (<30 kg/m², ≥30 kg/m²) at enrollment

All demographic and baseline characteristics will be presented in data listings.

4.7.2 Medical/Surgical History

Number (%) of subjects reporting Medical/Surgical history will be summarized by body system and report term.

Medical/Surgical History will also be presented in a data listing.

4.7.3 Baseline Physical Examination

Physical examination includes examination of general appearance; skin; head, eyes, ears, nose, and throat; thyroid; lungs; back; breasts; heart; abdomen; extremities; and neurological system.

Physical examination results indicating clinically significant abnormalities will be presented in a data listing.

4.7.4 Gynecological History

Gynecological history data will be summarized for all questions collected on the case report form (CRF).

All gynecological history will also be presented in a data listing.

4.7.5 Menstrual History

Menstrual history data will be summarized for all questions collected on the CRF.

All menstrual history will also be presented in a data listing.

4.7.6 Cervical Cytology

Cervical cytology test results will be summarized in the table and presented in a data listing.

4.7.7 Prior and Concomitant Medications

Prior and concomitant medications include any medications taken by subjects from 30 days prior to the signing of the informed consent through the end of study participation. These medications will be recorded on CRF page and coded using the WHO Drug dictionary. The CSR will include the version number of the WHO Drug dictionary. Prior medications are defined as those taken by the subject prior to the study device placement. Concomitant medications are defined as those taken by the subject from the date of the study device placement to study completion/discontinuation.

In cases where it is not possible to define a medication as prior or concomitant, the medication will be classified as concomitant.

The number (%) of subjects taking prior and concomitant medications will be summarized separately according to anatomical therapeutic chemical classification Level 4 and generic term for the ITT population.

All prior and concomitant medications will also be presented in a data listing.

4.8 Pearl Index Analysis

The pearl index will be utilized to measure contraceptive efficacy through 5 years of use and will be analyzed using the Pearl Index with a 95% CI for women in the EP population. A separate summary of the Pearl Index in the EP Population through Day 57 will also be provided.

The Pearl Index is defined as the number of on-treatment pregnancies per 100 women years. On-treatment pregnancy is defined as the estimated conception date being after the insertion date and no more than 7 days after the VeraCept is removed or expelled. One woman year is defined as comprising thirteen 28-day cycles.

$$\text{Point estimate of Pearl Index: } x \times \frac{1300}{E}$$
$$95\% \text{ CI: } \left(\frac{1}{2} \chi^2_{(0.025, 2x)} \times \frac{1300}{E}, \frac{1}{2} \chi^2_{(0.975, 2(x+1))} \times \frac{1300}{E} \right)$$

where x is the number of on-treatment pregnancies, E is the number of 28-day evaluable exposure cycles, and $\chi^2_{(p, df)}$ is the p th quantile of χ^2 -distribution with df degrees of freedom.

x =sum of PREGNANCY

E =number of Evaluable Cycles (NCYCEV)

Pearl Index point estimates and 95% CIs will be calculated for Day 57, Years 1, 2, 3, 4, 5, Years 1-2, Years 1-3, Years 1-4, and for Years 1-5 separately.

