4.1.5 Exposure Periods

The first exposure cycle starts on Day 1 of successful study device insertion. A full exposure cycle is comprised of 28 days. One woman-year comprises thirteen 28-day cycles. The following exposure periods are defined for analysis in terms of planned study days and study cycles to facilitate the efficacy and certain safety analyses.

Exposure Period	Study Day of Period Start (PSTDY)	Study Day of Period End (PENDY)
Year 1 (Cycle 1- Cycle 13)	1	364
Year 2 (Cycle 14-Cycle 26)	365	728
Year 3 (Cycle 27-Cycle 39)	729	1092
Year 4 (Cycle 40-Cycle 52)	1093	1456
Year 5 (Cycle 53-Cycle 65)	1457	1820
First 2 Years (Cycle 1-Cycle 26)	1	728
First 3 Years (Cycle 1-Cycle 39)	1	1092
First 4 Years (Cycle 1-Cycle 52)	1	1456
5 Years (Cycle 1-Cycle 65)	1	1820

Type of Events and Study Day During an Exposure Period

ETYPE	Event	Study Day of Event (EVTDY)
A	Expulsion	Study Day of Expulsion date
B	Expulsion followed by conception within 7 days	Study Day of Expulsion date
C	Removal	Study Day of Removal date
D	Removal followed by conception within 7 days	Study Day of Removal date
E	Pregnancy before expulsion	Study Day of Conception date
F	Pregnancy before removal	Study Day of Conception date
H	Lost to follow-up without pregnancy, expulsion, or removal	Study Day of Last Date Device in Situ
I	Complete period without pregnancy, expulsion, or removal	Study Day of Period End Date

Note: Removal due to partial expulsion will be treated as expulsion

Exposure Duration in Days (EXDUR):

if EVTDY-PSTDY>0 then EXDUR = min(EVTDY-PSTDY+1, PENDY-PSTDY+1);
 else EXDUR=.;

Exposure Duration in Cycles (NCYCF) = EXDUR/28

Number of Completed Cycles (NCYCC) = INT(NCYCF)

Number Relevant Cycles (NCYCR)

=NCYCC+1 if last partial cycle is \geq 23 days
 =NCYCC+1 if last partial cycle ETYPE is B, D, E, or F
 =NCYCC, otherwise.

Number of Evaluable Cycles (NCYCEV) =NCYCR

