4.1.6 Pearl Index

Pearl Index is defined as the number of on-treatment pregnancies per 100 women years. On -treatment pregnancy is defined as the estimated conception date being on or after the insertion date (must be a successful insertion) and no more than 7 days after the study device is removed or expelled. One women year is defined as comprising thirteen 28-day cycles.

$$\text{Point estimate of Pearl Index: } x \times \frac{1300}{E}$$

where x is the number of on-treatment pregnancies and E is the number of 28-day evaluable exposure cycles

If ETYPE is B or D or E or F, then PREGNANCY = 1; else PREGNANCY = 0

x = sum of PREGNANCY

E = Number of Evaluable Cycles (NCYCEV)

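### Safety SAP 4.8 and 4.1.6 disagree on a conception dated to the insertion day, and the exposure code loses the cycle of a pregnancy event on a period's first day (minor)

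*SAP*

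**What the plan says.** All passages are in the safety SAP.

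- **Start of the on-treatment window, derivation (4.1.6).** The rule is "the estimated conception date being on or after the insertion date (must be a successful insertion"; a conception on the day of successful insertion counts.
- **Start of the window, analysis (4.8).** "On-treatment pregnancy is defined as the estimated conception date being after the insertion date"; a conception on the insertion day does not count.
- **Numerator code (4.1.6, and summed in 4.8).** "If ETYPE is B or D or E or F, then PREGNANCY = 1; else PREGNANCY = 0". It depends on event type alone and does not test the insertion date.
- **EP population (4.2.1), criterion 3.** "Do not have pre-treatment pregnancy, which is defined as the estimated conception date being before the insertion date". A woman whose conception is dated to the insertion day stays in.
- **Study day (4.1.2).** The second reference date is the date of successful insertion: "The second study reference date is Day 1 of Cycle 1".
- **Exposure (4.1.5).** "if EVTDY-PSTDY>0 then EXDUR = min(EVTDY-PSTDY+1, PENDY-PSTDY+1"), and otherwise EXDUR is set to missing. For pregnancy before expulsion or removal (types E and F) the event day is the "Study Day of Conception date"; for types B and D it is the expulsion or removal day.
- **Cycle credit (4.1.5).** Relevant cycles equal "NCYCC+1 if last partial cycle ETYPE is B, D, E, or F", so a pregnancy event is meant to bring its partial cycle into the denominator.

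**The concern.** There are two faults, and they meet on the insertion day.

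First, under the text of 4.8 an insertion-day conception is neither pre-treatment nor on-treatment. The woman belongs to the EP population and her pregnancy goes nowhere. Under 4.1.6 it is an on-treatment pregnancy. Neither section says which one governs.

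Second, the strict inequality in the exposure code treats an event on the first day of a period as if it lay outside the period. The formula adds 1 to the day difference, so it plainly means a same-day event to give one day of exposure. The result instead is missing, and the pregnancy cycle credit built on it is missing too.

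Section 4.4 shows the EP population for VeraCept only, and 20 VeraCept women are planned, so one pregnancy may be the whole numerator. Conception dates are estimates. If the boundary case arose, someone would have to choose a rule after seeing the pregnancy, which a prespecified plan should prevent.

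**Working it through.** **1. Reproduce the plan's own figures.** Section 4.1.5 gives Years 1-5 as Days 1 to 1820. For a woman who completes the period, EXDUR = 1820 and 1820/28 = 65 cycles, as tabulated. One year is 364/28 = 13 cycles, so 100 woman-years are 1300 cycles, the multiplier in the Pearl Index x × 1300/E. The documents give no expected value for the index.

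**2. Set the start rules side by side.**

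| Conception dated | 4.1.6 text | 4.8 text | EP criterion 3 | PREGNANCY code (type E or F) |
|---|---|---|---|---|
| Before insertion | not counted | not counted | excluded | not applied |
| On the insertion day | counted | not counted | kept | 1 |
| Later, device in place | counted | counted | kept | 1 |

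Only the middle row differs, and there the text of 4.8 stands alone.

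**3. Run the exposure code with EVTDY = PSTDY.** The difference is 0, which fails the >0 test, so EXDUR, NCYCF, NCYCC and NCYCR are all missing. PREGNANCY is still 1. With >=0 and a Day 1 event in Years 1-5:

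- EXDUR = min(0+1, 1820-1+1) = 1 and NCYCC = INT(1/28) = 0.
- Types B, D, E and F: NCYCR = 0+1 = 1, so E gains one cycle.
- Types A, C and H: one day is below the 23-day threshold, so NCYCR = 0 and E does not change.

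An event before the period still gives missing under >=0, as it should.

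**4. Illustration.** Assumptions: 20 EP women, one type E or F conception on the insertion day, the other 19 completing the period. For Day 57 the period is taken as Days 1 to 57, so INT(57/28) = 2 cycles each. Intervals use the 4.8 formula.

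| Reading | Years 1-5 | Through Day 57 |
|---|---|---|
| 4.8 text, x = 0 | 0 (upper limit 3.88) | 0 |
| 4.1.6, code as written | 1300/(19×65) = 1300/1235 = 1.053 (0.027 to 5.865) | 1300/(19×2) = 1300/38 = 34.2 (0.87 to 190.6) |
| 4.1.6, code with >=0 | 1300/1236 = 1.052 (0.027 to 5.860) | 1300/39 = 33.3 (0.84 to 185.7) |

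With 12 EP women the Years 1-5 values are 0, 1300/715 = 1.818 and 1300/716 = 1.816.

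**5. Later periods.** Every cumulative period starts on Day 1, so Days 365, 729, 1093 and 1457 matter only for the single-year indices. The start rules agree there, and only the exposure code acts. For a Day 365 conception in the Year 2 index, with 19 others completing, the value is 1300/247 = 5.263 as written and 1300/248 = 5.242 corrected.

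**6. Away from the boundary.** A Day 100 conception gives INT(100/28) + 1 = 4 cycles and 1300/(1235+4) = 1.049 under every reading.

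**The case against.** The written algorithm already points one way. Section 4.8 sums PREGNANCY, whose only derivation is in 4.1.6 and has no insertion-date test. The 4.1.6 text, the code and the EP exclusion all agree; one sentence in 4.8 is the outlier. The value 0 arises only if that sentence is read as overriding the formula in its own section. This stands, and it shows which text to change, but a programmer could still filter on the sentence as written.

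The case is also unlikely. The protocol excludes women at risk from unprotected intercourse earlier in the cycle (4.2), requires one of three criteria for being reasonably certain of non-pregnancy (Box 2), and has a urine test before placement (6.1.2). These lower the chance of an insertion-day conception without ruling it out.

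The stakes are low. The Pearl Index was added by the safety SAP (Section 5) and is not a protocol endpoint. Section 4.10 says there is no formal efficacy analysis. Pregnancies are listed (4.11.8) and narrated (4.11.3), so the case would stay visible. With intervals this wide, the third-decimal effect of the exposure code carries no information. All of this stands and limits the priority.

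A reader might go further and infer that the exposure code is a second definition of the index, or that it gives a wrong index for any first-day event. Neither holds. As written it gives one determinate result, missing, and correcting it changes E only for pregnancy-type events, by one cycle each.

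**Conclusion.** Both faults are in the current text, and both matter only at a boundary. The start rules differ only for a conception dated to the insertion day; there they move the numerator by one pregnancy. The exposure condition costs one cycle of E per pregnancy-type event on the first day of a period, unless records with missing exposure are dropped, in which case the pregnancy would be lost from the numerator as well.

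A reader might infer that the Pearl Index is ambiguous in general. The documents do not support that: without such an event every reading gives the same value. Nor should the size be worked out by giving the pregnant woman full exposure (1300/40 = 32.5 through Day 57, 1300/1300 = 1.0 over five years), because neither rule credits her with those cycles.

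The illustrated values rest on assumed numbers of women and on full follow-up of the others. Twenty is an upper bound, because 20 VeraCept women are planned and the EP population stops at age 35. The primary pharmacokinetic results are unaffected. The priority is minor.

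**What to change.** 1. In Section 4.8, count a conception dated on or after the date of successful insertion. This matches 4.1.6 and leaves no gap with the EP exclusion.
2. In Section 4.1.5, change the condition to EVTDY-PSTDY>=0, so that an event on the first day of a period gives one day of exposure and a pregnancy event on that day receives its cycle.

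The cost is two edits to text and code, with no new data. The first edit can only raise the index or leave it unchanged. The second, taken alone, lowers it trivially when it acts at all, as in 1.053 to 1.052 above. Both should be made before the affected outputs are run, so that neither choice depends on an observed pregnancy.
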